6.5.1.2 Secondary End-Point Analysis: Histology And Endoscopy

At the end of each phase, we will employ generic Health Related QOL metrics, such as PROMIS General Health Questionnaire and Peds-QL and eventually compare the changes in disease specific versus general health questionnaires. These PROs will be assessed at the screening visit and again at the end of each treatment phase to assess the effects of treatment. All participants will undergo EGD with biopsy and the percentage of patients who have <15 peak eosinophils/hpf will be determined. The slides will be reviewed by local pathologists for clinical purposes, who will be blinded to the treatment group and patient study number. The local pathology review will be used to determine whether or not participants continue into Phase II of the study. Participants with ≥ 15 peak eosinophils/hpf who were on 4FED during Phase I will continue into Phase II to receive SGC for three months while on an unrestricted diet. Participants with ≥ 15 peak eosinophils/hpf who were on 1FED during Phase I will also continue into Phase II, but will maintain the 4FED therapeutic diet for 3 months. The Central Review Pathology Committee (CRPC), who will also be blind to the treatment group, will subsequently review the esophageal biopsy slides to determine other parameters (such as the Histology Scoring System (HSS)). CRPC review will be completed, whenever possible, within 2 weeks of a subject's endoscopy. . Participants who achieve histologic remission at the end of Phase I (as determined by the local pathology review) will have completed the study and will resume follow-up care with their primary gastroenterologist or allergist. Peak eosinophil change will be measured and we will also aim to determine the percentage of patients who achieve remission, defined as both complete remission (≤ 1 peak eosinophils/HPF) and partial remission (<10 and <6 peak eosinophils/HPF) as reported¹¹; this will allow us to compare with other studies that have used 6FED^{16, 19, 25, 26}. Furthermore, we aim to more broadly examine the impact of each therapeutic intervention on other histological parameters associated with EoE using a quantitative histology scoring system (HSS) that has been developed by our expert pathologist, [name]. The HSS evaluates esophageal biopsies for various features (ex: basal layer hyperplasia, dilated intercellular spaces, surface epithelial alteration, apoptotic epithelial cells), eosinophilic inflammation (peak count, eosinophil abscess, eosinophil surface layering), and lamina propria (fibrosis). For central review, slides of relevant esophageal biopsies obtained during the course of the study will be scanned using an Aperio Imaging scanner and viewed by the CRPC using Aperio Imaging Software. Each member of the CRPC has access to an Aperio scanner in his or her pathology department and to the Aperio Imaging Software. Slides may be scanned into Aperio at the local site, or they may be sent to Cincinnati Children's Hospital Medical Center (CCHMC) to be scanned into Aperio (if the local site does not have an Aperio scanner). These slides will be returned to the local site once they have been

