1 INTRODUCTION

Pertaining to the objectives of the protocol, this statistical analysis plan (SAP) specifies, prior to finalization of study database, a comprehensive description of strategies and statistical techniques that are planned to assess clinical efficacy and safety of 1 food elimination (milk elimination alone, 1FED) versus 4 food elimination (milk, egg, wheat, and soy elimination, 4FED) diet intervention of Eosinophilic Esophagitis (EoE), and the following Glucocorticoids treatment.

The primary objective of this protocol is to conduct a prospective, non-blinded randomized trial comparing patient reported outcomes scores in novel empiric elimination dietary therapies in eosinophilic esophagitis (EoE) in order to assess the therapeutic viability of minimally restrictive empiric elimination diets as related to measures of patient's symptoms, quality of life, and pathology. The primary efficacy outcome will be the change in the standardized and validated Pediatric Eosinophilic Esophagitis Symptom Score v2 (PEESS).

Moreover, we also aim to assess the response to topical swallowed steroids in those who were non-responders to empiric dietary therapy regimens used during the initial phases of this study.

A variety of secondary endpoints, including pre- and post-therapy peak eosinophil counts per hpf and percentages of patients that attain histologic remission (<15 eosinophils/hpf), along with detailed histologic and endoscopic scores, novel biomarkers, and patient related outcome (PRO) measures will be analyzed between treatment groups.

In addition, we will assess the possible value of a variety of clinical characteristics and biomarkers in terms of predicting response to therapy. Relationship between PEES response and histologic response will be investigated as well to better understand PRO measures in predicting disease status.

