1.2 Secondary Objectives

- To extend Phase I of this study with a prospective non-blinded trial that determines the rate of remission after treatment with 4FED (in participants failing 1FED in Phase I) or SGC (in participants failing 4FED in Phase I) (Phase II).
- To evaluate the effect of each therapy on histological remission (defined as a post therapy eosinophil count of <15 eosinophils/HPF) and by a variety of changes in eosinophils, including (a) pre- and post-therapy peak eosinophil counts; (b) partial remission (2-14 peak eosinophils/hpf); and (c) complete histological remission (≤ 1 peak eosinophils/hpf).
- To evaluate the effect of each therapy by utilizing the histology scoring system (HSS) created to express the severity and extent of other abnormalities in the gastrointestinal (GI) tract that often accompany eosinophilic inflammation.
- To determine the impact of each therapeutic intervention on biomarkers using the EoE Diagnostic Panel (EDP).
- To evaluate the clinical and psychosocial effect of each therapy using the Peds Quality of Life Inventory Eosinophilic Esophagitis Module (PedsQL EoE) to assess EoE symptoms and problems/feelings related to eating.
- To determine if any clinical parameters predict response to therapeutic intervention.
- To determine if any biomarkers including component-resolved diagnostics (CRD) [serum IgE component testing] predict response to therapeutic intervention.
- To determine if skin testing, in the form of prick and patch testing, predicts response to therapeutic intervention.
- Also to assess relationship between primary PEES score changes and histological scores (HSS).

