4 STUDY PARTICIPANTS

4.1 Number of Participants

A total of 292 participants between the ages of 6-17 years were to be enrolled. Because of unexpectedly slow

enrollment, the actual number of participants will be around 50 total. The DMCC at the University of South Florida Health Informatics Institute will serve as the central data management center, with CCHMC serving as the primary site and the central IRB. Additional sites include: Children's Hospital of Colorado, Riley Hospital for Children, Children's Hospital of Philadelphia, University of California at San Diego/Rady Children's Hospital, Northwestern University/Lurie Children's Hospital, Tufts Medical Center, Mt. Sinai Kravis Children's Hospital, Arkansas Children's Hospital, and the University of North Carolina.

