 - Percent of participants who achieve histologic remission (<15 peak eosinophils/HPF) post therapy assessed after the end of the 3 months
 - Division of patients into complete (all peak eosinophils ≤1/HPF) or partial (the worse of 3 scores is from 2 to 14) remission, and non-remission (at least one > 14/HPF)
 - Histology Scoring system
 - Endoscopic scoring system (EREFS)
- Biomarkers pre- and post-treatment
 - Assessment of Eosinophil Diagnostic Panel EoE Score
- Clinical parameters and biomarkers to predict responsiveness to diet and SGC therapy

- Correlation of clinical characteristics to response to therapy
- Assessment of predictive value of skin prick and patch allergy skin testing
- Correlation between presence of positive milk component allergy testing to response to 1FED
- Predictive biomarker-analysis of EoE transcriptome from EDP analysis on baseline biopsies in correlation to response to treatment.

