6 STATISTICAL METHODS

6.1 Statistical Analyses: Aim 1

Demographic and patient characteristics will be summarized for the two treatment groups using mean \pm standard deviation or median [interquartile range] for continuous variables and frequency and percentages for categorical variables. Treatment comparisons will be performed using the two-sample t-test or Wilcoxon Rank sum test for continuous variables and the Fisher's Exact test for categorical variables. All tests will be conducted at $\alpha=0.05$, including the primary and secondary analyses.

There was going to be two sets of analysis populations in terms of efficacy assessment, the intent-to-treat and per protocol. However, since the total enrollment has been reduced to about 50, all patients randomized to Phase I of the study who have at least one clinical observation post randomization will be considered in intent-to-treat set. Only this set of population will be included in the statistical analyses. Originally, we plan to define patients who are at least 80% compliant to dietary assignment during Phase I, and who do not have any major protocol violations as in per protocol set. Now all analyses will be based on intent-to-treat population. Patients who do drop out of the trial before the end of Phase I will have their PEES done at the time of dropout. The primary endpoint is overall PEES score change from pre-treatment to the end of Phase I. If normality assumption is approximately valid, a linear mixed effect model will be applied to the primary efficacy variable,

account for site random effect, and other potentially important covariates, e.g. gender, race, and PPI use etc. Because of non-normal nature of the scores in previous research, a Wilcoxon rank sum test may be applied to compare between two treatment groups when normality is violated.

As a secondary endpoint analysis, remission rates (as defined by the percentage of participants achieving histologic remission (eosinophils less than 15/HPF) at the end of Phase I will be analyzed in the following 3 steps.

- (1) Remission rates will be computed along with their 95% CIs for each diet group separately;

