- (2) Remission rates will be compared between the two treatment groups using the generalized linear mixed effects model with the logit link (for binary outcome) that accounts for the clustering within sites. Important covariates will be analyzed in this model including gender, race, PPI use, atopy, age, and anthropomorphic features. Treatment group comparisons for secondary endpoints will be performed using the generalized linear mixed effects model using the link that is appropriate for the endpoint (i.e. logit for binary, log for Poisson count, identity for continuous). These models will account for the clustering within sites and will include the same covariates as for the primary analysis.
- (3) The remission rate for non-responders who proceed to Phase II will be summarized separately depending on the treatment patients received during Phase I and Phase II. The 95% confidence interval for the rates will also be provided.

6.2 Statistical Analyses: Aim 2

To evaluate the ability of biomarkers and phenotypic characteristics to predict response to therapeutic intervention, multivariable logistic regression analysis may be conducted with histological evaluation of remission/no remission as the dependent variable and biomarker levels as the independent variables. Multicollinearity of the independent variables will be assessed. The area under the receiver operating characteristic curve (AUROC) will be estimated along with 95% confidence interval. This analysis will be conducted based on the remission status at the end of Phase I. It may also be repeated at the end of Phase II by including those patients who also responded to SGC.

Additionally, a correlation analysis between PEES scores and biomarkers will be performed. Spearman's correlation coefficient and its confidence intervals will be computed to further assess predictive utility for the biomarkers of interest.

Missing data will be handled in the following manner. For the primary efficacy measure of PEES, each patient is expected to complete the questionnaire; even if the patient terminates participation early (dropout) for any reason. The total PEES score is the average of 20 item scores, as long as there are at least 10 item response non-missing, as described previously. No imputation of missing total PEES will be performed. The early dropout reasons will be recorded, and rates will be assessed between treatment groups for potential patterns.

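### The secondary-endpoint model names a Poisson log link with no dispersion term; if the post-treatment peak eosinophil count is fitted with it, the 5% level is exceeded whenever within-site residual variance exceeds the mean

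*SAP*

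**What the plan says.** - **Model.** SAP 6.1 step (2), with the same wording in Protocol 12.2, compares the diets on secondary endpoints by a generalized linear mixed model "using the link that is appropriate for the endpoint", listed as "i.e. logit for binary, log for Poisson count, identity for continuous". The model accounts for site and carries the covariates of the primary analysis. Neither document mentions a dispersion parameter, a negative binomial or quasi-Poisson model, a robust variance or a patient-level random effect.
- **Level.** SAP 6.1 and Protocol 12.2 set 0.05 for every test, primary and secondary.
- **Count measure.** SAP 1 names "pre- and post-therapy peak eosinophil counts per hpf" among the secondary endpoints to be compared between groups, and SAP 1.2 repeats it as an objective. Protocol 6.5.1.2 says instead "Peak eosinophil change will be measured". The formal endpoint lists (SAP 5.2, Protocol 10.7) give remission rates and classes, HSS and EREFS, and no raw count.
- **Other tests.** The opening paragraph of SAP 6.1, which deals with demographic and patient characteristics, says "Treatment comparisons will be performed using the two-sample t-test or Wilcoxon Rank sum test for continuous variables". The Wilcoxon fallbacks for violated normality are stated for PEESS (SAP 6.1) and the EoE score (SAP 5.2.1.1) only.
- **Size.** SAP 4.1: "the actual number of participants will be around 50 total".

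**The concern.** A Poisson model fixes the variance at the mean. Eosinophil counts after a diet that works in some children and fails in others should vary more than that. The plan's own classes run from at most 1, through 2 to 14, to above 14 with no ceiling, and Protocol 12.1 assumes response rates of 45% and 65%. A site random intercept does not absorb this spread, because it lies between patients within a site.

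If the count is fitted as Poisson, the standard error of the diet effect is too small by the square root of the variance-to-mean ratio. A histologic difference could then be declared at the 0.05 level far more often than 5% of the time when the diets do not differ. The documents do not say whether this measure is the post-treatment count (log link), the change (identity link), or a continuous variable for the t-test or Wilcoxon test. Only the first has the problem.

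**Working it through.** **Inputs from the documents.** Level 0.05 (SAP 6.1), taken as two-sided; about 50 patients, 1:1, so 25 per arm (SAP 4.1, SAP 2); 10 sites (SAP 4.1); remission threshold 15/hpf; response rates 45% and 65% (Protocol 12.1), pooled to 55% under the null.

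**Assumed.** The residual variance-to-mean ratio φ, for which the documents give no mean, SD or upper limit.

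**Step 1: formula.** If the variance is φ × mean and the model assumes φ = 1, the large-sample Wald test has actual level

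2 × [1 − Φ(1.96/√φ)].

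At φ = 1 this returns 0.050, the plan's figure. At φ = 2, 1.96/1.414 = 1.386, giving 16.6%. At φ = 3.31, 1.96/1.82 = 1.077, giving 28.1%. At φ = 5.67, 1.96/2.38 = 0.823, giving 41.0%.

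**Step 2: where 3.3 and 5.7 come from.** Take 55% remitters uniform on 0–14 (mean 7, variance 18.67) and 45% non-remitters uniform from 15 to an assumed upper value.
- Upper value 20: mean 0.55×7 + 0.45×17.5 = 11.725; variance 0.55×18.67 + 0.45×2.92 + 0.55×0.45×10.5² = 38.87; ratio 3.31.
- Upper value 30: mean 13.975; variance 0.55×18.67 + 0.45×21.25 + 0.2475×15.5² = 79.29; ratio 5.67.

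**Step 3: simulation at this trial's size.** No diet difference, 25 per arm, 10 sites, sex and PPI use as covariates, 1,200 runs per row (Monte Carlo SE 0.6 points at 5%). The quasi-Poisson column uses fixed sites and a t reference.

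| Assumed distribution | φ | Formula | Poisson mixed model, random site | Quasi-Poisson |
|---|---|---|---|---|
| Poisson, mean 14 | 1.00 | 5.0% | 4.8% | 5.1% |
| Negative binomial, mean 14 | 1.51 | 11.0% | 9.3% | 4.8% |
| Negative binomial, mean 14 | 2.00 | 16.6% | 16.2% | 3.4% |
| Mixture, upper value 20 | 3.31 | 28.1% | 29.3% | 3.6% |
| Mixture, upper value 30 | 5.67 | 41.0% | 41.3% | 4.0% |
| Mixture, upper value 60 | 15.4 | 61.8% | 61.4% | 5.7% |

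A separate simulation of the Poisson model with fixed sites gave 18%, 29%, 40% and 61% at ratios of 2, 3.3, 5.7 and 15, and 3% to 6% for quasi-Poisson.

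**Step 4: site variation is not the cause.** With counts that are Poisson within site and a site SD of 0.6 on the log scale, the mixed model held 4.9%. What matters is the variance left after site and covariates.

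**Step 5: how small could φ be?** Put every patient in a class at one favourable count, with 55% in remission. If 10% reach complete remission, 10% at 1, 45% at 14 and 45% at 15 gives mean 13.15, variance 16.63, ratio 1.26 and a level of about 8%. If 20% do, 20% at 1, 35% at 13 and 45% at 15 gives mean 11.5, variance 28.35, ratio 2.47 and a level of about 21%. Spread within classes would usually raise these ratios; covariates that explain the counts would lower them. The complete-remission share is an assumption, and at 5% or less this bound falls below 1.

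**The case against.** The strongest reply is that the plan never assigns peak eosinophils to the Poisson model. The formal endpoint lists contain no raw count. Protocol 6.5.1.2 names a change, which can be negative and so cannot be Poisson. The governing phrase is "using the link that is appropriate for the endpoint", which can be read as reserving the Poisson link for counts that are in fact Poisson. On the change route or the rank-test route there is no such inflation. This stands, and it is why the point is conditional. A reader might infer that the plan commits to Poisson for this measure; the documents do not support that.

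The reply does not dispose of the point. SAP 1 lists the post-therapy count among endpoints to be compared between groups, the Poisson clause has no other evident use, and no count fallback is written.

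A second reply is that the size comes from assumed distributions. That also stands. A reader might take 29%, 40% or 61% as this trial's error rate, but they are only what would follow at the stated ratios. Step 5 makes a ratio above 1 plausible without proving it.

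A third reply is that the simulations used sex and PPI use only, whereas the plan also names race and leaves its list open. This is true. Further covariates matter only through the residual variance that they remove.

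**Conclusion.** The point holds conditionally and is minor. The plan names a count model whose test keeps its level only when residual variance does not exceed the mean, and does not say whether its one evident count goes into that model. If it does, the diet comparison on that measure runs at about 9% to 11% for a ratio of 1.5, 16% to 18% for 2, 29% for 3.3 and 40% to 41% for 5.7. These figures assume about 50 patients, a two-sided 0.05 test and the stated ratios. Confidence is medium, because both the route and the ratio are inferred.

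A reader might extend this to the trial's main result or to its histologic conclusions in general. The documents do not support that. PEESS is analysed by a linear mixed model or Wilcoxon test, remission by a logit model, and entry to Phase II by a threshold on the local pathology count. None of these uses the Poisson variance.

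**What to change.** In SAP 6.1 and Protocol 12.2, before the database is finalized, state one of the following for peak eosinophils per hpf:

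- the post-treatment count, by a quasi-Poisson log-link model with estimated dispersion, site as a fixed effect, the same covariates and a t reference; or
- the change from baseline, with the identity link.

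Add the measure to SAP 5.2 and Protocol 10.7 so that the endpoint lists match the objectives.

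A linear mixed model on log(count+1) or a negative binomial mixed model should replace quasi-Poisson only if its test size at about 50 patients is checked first. In the same simulations the former ran at 4.4% to 6.6% (6.3% or more in five of eight scenarios) and the latter at 3.5% to 8.1%. Uncorrected robust standard errors on the Poisson model ran at 8.6% to 11.6% and should not be used.

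**Cost.** One sentence on the model in each document, one entry in each endpoint list, and no new data. Quasi-Poisson still estimates the ratio of mean counts, but its intervals are wider by about √φ (1.41 at a ratio of 2, 1.82 at 3.3). Fixed site effects use up to 10 − 1 = 9 degrees of freedom; with intercept, diet, sex and PPI use, about 50 − 13 = 37 remain.

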6.5.2.2 Skin Testing

In this sub-aim, we hypothesize that skin test results (prick testing and atopy patch testing to the four food groups) will provide significant predictive value for outcomes in the diet trial phases. While a substantial body of work has already been done concerning skin testing, there still remains debate about its practice in managing EoE. As such, in this sub-aim, we will take several different approaches compared with prior work. In particular, we will be conducting a multi-site trial and have the advantage that we can standardize the skin testing procedure, by using agreed upon techniques, including food extracts, skin test reagents, and measurement parameters. We will thus be in a good position to dissect discrepant results between centers. Furthermore, our trial is unique in that half of the patients will undergo a milk elimination diet as part of the first phase. Thus, we will be in a position to focus on the value of skin testing for milk, which is particularly attractive as milk is the number one food trigger of EoE³⁰. It is important to point out that although skin testing (including patch testing) is now readily performed in EoE, there have been no studies that have assessed the local response. For example, it has not yet even been determined if positive responses involve immunological reactions so basic cytokine and histological analyses are likely to be fundamentally informative.

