6.5.2.4 Predictive Biomarker-Analysis Of EoE Transcriptome

In this sub-aim, we aim to identify biomarkers that may predict responsiveness to any or all of the treatment interventions associated with this trial. Determining such a biomarker would have a profound effect on disease management as patients could be quickly triaged into different therapies, e.g. diet versus SGC; thus saving time, reducing the number of endoscopies and potentially improving quality of life issues. As such, in this sub-aim, we will perform the EDP analysis on baseline biopsies, focused on identifying transcript levels that differentiate patients that respond to each of the interventions. In preliminary studies, we have conducted this type of analysis on patients that recently participated in the randomized controlled trial of high dose fluticasone (1760 mcg per day) for the treatment of EoE. Forty-two participants were enrolled in this study (28 FP, 14 placebo). After 3 months, 65% of FP-treated and 0% of placebo-treated participants had complete remission ($P = 0.0001$);

12% of FP-treated and 8% of placebo-treated participants had partial remission. Of the FP-treated participants in complete remission, 73% continued in complete remission, and 20% were in partial remission after halving the daily FP dosage³⁷.

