12 STATISTICAL METHODS

12.1 Sample Size Calculation

Sample size was determined based on the primary endpoint of the trial: The overall PEES score change from pre-treatment. Based on a preliminary report¹⁸ we estimate that 40-50% of patients may respond to 1FED as our study is prospective compared with 65% response in this preliminary retrospective report and based on food reintroduction trial results³⁰. Likewise, we would expect 75% of patients to respond to 6FED based on the previously reported studies, and from this we extrapolated a projected response of 65% to 4FED, given that the 4 eliminated foods are consistently identified as the most common triggering antigens³⁰. As such, we estimate that 45% of patients will respond to 1FED and wish to detect an additional 20% increase for the 4FED (i.e. 65% response rate). A non-parametric Wilcoxon rank sum test will be applied for the primary efficacy endpoint comparison. We are assuming a difference in response rate of 45% vs 65% between the two treatment groups, and we further assume that those who respond to 1FED will naturally respond to 4FED. We also assume that those who responded will have a higher PEES score change than those who do not respond. Then the estimated probability of 4FED scores higher than 1FED is about 0.60 ($= 0.5 \times \text{prob. of response to both or neither} + 1.0 \times \text{incremental response rate from 1FED to 4FED}$). This will require 131 patients per group to reach 80% power at 0.05 test level. By accounting for a 10% early dropout rate, we propose a sample size of 146 per group, or 292 total patients to be enrolled.

12.2 Statistical Analyses: Aim 1

Demographic and patient characteristics will be summarized for the two treatment groups using mean \pm standard deviation or median [interquartile range] for continuous variables and frequency and percentages for categorical variables. Treatment comparisons will be performed using the two-sample t-test or Wilcoxon Rank sum test for continuous variables and the Fisher's Exact test for categorical variables. All tests will be conducted at $\alpha=0.05$, including the primary and secondary analyses.

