clustering within sites and will include the same covariates as for the primary analysis. The remission rate for non-responders who proceed to Phase II will be summarized separately depending on the treatment patients received during Phase I and Phase II. The 95% confidence interval for the rates will be provided.

12.3 Statistical Analyses: Aim 2

To evaluate the ability of biomarkers and phenotypic characteristics to predict response to therapeutic intervention, multivariable logistic regression analysis will be conducted with histological evaluation of remission/no remission as the dependent variable and biomarker levels as the independent variables. Multicollinearity of the independent variables will be assessed. The area under the receiver operating characteristic curve (AUROC) will be estimated along with 95% confidence interval. This analysis will be conducted based on the remission status at the end of Phase I. It will be repeated at the end of Phase II by including those patients who also responded to SGC.

A sample size of 292 total patients will provide at least 80% power to detect an AUROC of 0.60. This calculation is based on the assumption that 161 patients (66 1FED, 95 4FED) will be in remission at the end of Phase I (and therefore not move on to phase II) and 131 patients will not be in remission (with an estimated 10% dropping out and not continuing on to Phase II).

Additionally, a correlation analysis between PEES scores and biomarkers will be performed. Spearman's correlation coefficient and its confidence intervals will be computed to further assess predictive utility for the biomarkers of interest.

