5.2.2 AIM 2: Clinical Parameters & Biomarkers That Predict Therapeutic Response

5.2.2.1 Predictive Biomarker-Analysis Of EoE Transcriptome

In this sub-aim, we aim to identify biomarkers that may predict responsiveness to any or all of the treatment

interventions associated with this trial. As such, in this sub-aim, we will perform the EDP analysis on baseline biopsies, focused on identifying transcript levels that differentiate patients that respond to each of the interventions.

Baseline esophageal gene expression was compared between responders and non-responder patients by statistically screening two cohorts. A list of genes with $p < 0.05$ (or $FDR < 0.05$), fold change > 2.0 will be identified.

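### The Phase I Aim 2 model pools the two diets with no diet term or marker-by-diet interaction, so it cannot report marker performance by diet, and a marker specific to 4FED-only responders could nearly cancel

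*SAP*

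**What the plan says.** **The aim is specific to each intervention.** Protocol 6.5.2.1 sets out to relate patient characteristics to response to 1FED, 4FED and SGC. Protocol 6.5.2.4 wants baseline biopsies used for "identifying transcript levels that differentiate patients that respond to each of the interventions", so that patients can be directed to one therapy or another. Protocol 6.5.2.2 hypothesises that skin tests "will provide significant predictive value for outcomes in the diet trial phases".

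**The model is not.** SAP 6.2 states that a "multivariable logistic regression analysis may be conducted with histological evaluation of remission/no remission as the dependent variable and biomarker levels as the independent variables", and adds: "This analysis will be conducted based on the remission status at the end of Phase I". At that point both randomised diets are in the data. Neither a diet term nor an interaction is named.

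**Protocol 12.3 shows the pooling.** "A sample size of 292 total patients will provide at least 80% power to detect an AUROC of 0.60", on the assumption that "161 patients (66 1FED, 95 4FED) will be in remission at the end of Phase I" and that the other 131 will not.

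**The transcript screen is unclear.** SAP 5.2.2.1 repeats the aim of finding markers for each intervention, then describes the method as: "Baseline esophageal gene expression was compared between responders and non-responder patients by statistically screening two cohorts". It does not say whether this is done within diet.

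**Two related provisions.** The milk-component analysis (SAP 5.2) is restricted to response to 1FED. The closing paragraph of SAP 6.2 allows optional tests of interaction between treatment and demographic or baseline characteristics, in the generalized linear mixed models.

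**The concern.** Both diets remove milk; 4FED also removes egg, wheat and soy. A child whose disease is driven by one of those three foods would be expected to fail 1FED and remit on 4FED. A marker of such children points towards failure in one arm and towards remission in the other. A model with a single marker coefficient averages the two directions.

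More generally, a reader choosing between the diets needs to know how a marker performs on each. The pooled AUROC answers a different question: whether the marker separates remitters from non-remitters in an equal mixture of the two diets.

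**Working it through.** **Inputs.** Protocol 12.1: "we estimate that 45% of patients will respond to 1FED and wish to detect an additional 20% increase for the 4FED", i.e. 65% on 4FED, together with the assumption that everyone who responds to 1FED also responds to 4FED. This gives three classes: A, responds to both diets (45%); B, responds to 4FED only (20%); C, responds to neither (35%). Allocation is 1:1. Planned N is 292 (Protocol 12.1); expected N is about 50 (SAP 4.1). The test level is 0.05, taken as two-sided because the documents do not say.

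**Step 1: reproduce the stated Aim 2 power.** 146 × 0.45 = 65.7 (66) and 146 × 0.65 = 94.9 (95), so 161 remitters and 292 − 161 = 131 non-remitters.
- Null SE of the AUROC: √[(161 + 131 + 1)/(12 × 161 × 131)] = 0.0340.
- SE at 0.60 (Hanley-McNeil, Q₁ = 0.6/1.4 = 0.4286, Q₂ = 0.72/1.6 = 0.45): √{[0.24 + 160(0.4286 − 0.36) + 130(0.45 − 0.36)]/(161 × 131)} = 0.0330.
- Power: Φ[(0.10 − 1.96 × 0.0340)/0.0330] = 84%. With 10% loss (145 v 118) it is 80%.

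The stated figure reproduces, and it does so on the pooled split.

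**Step 2: a perfect yes/no marker of class B.** For a binary marker, AUROC for remission = 0.5 + [P(+ | remission) − P(+ | no remission)]/2.

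| Data | P(+ given remission) | P(+ given no remission) | AUROC |
|---|---|---|---|
| 1FED | 0 | 0.20/0.55 = 0.364 | 0.32 |
| 4FED | 0.20/0.65 = 0.308 | 0 | 0.65 |
| Pooled | 0.20/1.10 = 0.182 | 0.20/0.90 = 0.222 | 0.48 |

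An AUROC of 0.32 for remission is 0.68 for failure. At sensitivity and specificity 0.8 the three values are 0.39, 0.59 and 0.49.

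**Step 3: markers that do not cancel.** A perfect marker of class A is positive in 0.90/1.10 = 82% of pooled remitters and in no non-remitters, giving a pooled AUROC of 0.91 (1.00 on 1FED, 0.85 on 4FED).

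For a graded marker, normal with SD 1, AUROC = Σᵢ Σⱼ uᵢ vⱼ Φ[(mᵢ − mⱼ)/√2]. Here u and v are the class shares among remitters and non-remitters, and m is the class mean. The shifts below are assumptions; the documents give none.

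| Shift in B, C (A = 0) | 1FED | 4FED | Pooled |
|---|---|---|---|
| 1 SD, 0 | 0.41 | 0.58 | 0.49 |
| 1 SD, 0.5 SD | 0.32 | 0.45 | 0.38 |
| 1 SD, 1 SD | 0.24 | 0.32 | 0.29 |

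Read as AUROC for failure, the second row is 0.68 on 1FED, 0.55 on 4FED and 0.62 pooled. The marker survives, but the pooled value describes neither diet.

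**Step 4: power** (2,000 simulated trials per case, likelihood-ratio tests).

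| Shift in B, C | N | Pooled marker test | Marker-by-diet test |
|---|---|---|---|
| 1 SD, 0 | 292 | 6% | 74% |
| 1.5 SD, 0 | 292 | 6% | 97% |
| 1 SD, 0 | 50 | 6% | 19% |
| 1.5 SD, 0 | 50 | 5% | 34% |
| 1 SD, 0.5 SD | 292 | 93% | 54% |
| 1 SD, 0.5 SD | 50 | 30% | 17% |

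At N = 50 the planned split scales to about 28 remitters (50 × 161/292 = 27.6) and 22 non-remitters. Power for a pooled AUROC of 0.60 is then about 22% by the Step 1 formula.

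**The case against.** Four points on the other side carry weight.

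- **Cancellation is a special case.** It needs a marker raised in the 20% and not in the 35%. Nothing in the documents says that markers behave this way. This stands.
- **The marker set only partly fits the scenario.** The named components are for egg and milk, with other foods tested when indicated (Protocol 6.5.2.3). Patch testing is for milk only, although prick tests cover all four foods (Protocol 7.3). This stands: only some of the markers are exposed.
- **SAP 6.2 already allows interactions.** Baseline markers could be read as baseline characteristics, and the mixed remission model has the same outcome as Aim 2. But the clause is optional, names no biomarkers, and changes neither the Aim 2 logistic model nor its AUROC. It softens the point without answering it.
- **With about 50 patients the interaction test would usually miss the marker too.** This is true, and it decides how results should be reported. It does not make the pooled model an answer to the by-diet question.

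Three stronger readings are tempting and should be resisted. A reader might infer that Aim 2 cannot show who does well on milk removal alone; Step 3 contradicts this, since a marker of milk responders keeps a pooled AUROC of 0.91. A reader might infer that any informative egg, wheat or soy marker would be reported as non-predictive; that fails once the marker is also raised in those who respond to neither diet. A reader might infer that the transcript screen is definitely pooled; SAP 5.2.2.1 is silent on this, and its stated aim refers to each intervention.

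**Conclusion.** The concern holds in a limited form. The Phase I Aim 2 model pools the diets with no diet or interaction term, while its aim is specific to each intervention. It would return one averaged effect per marker. For a marker confined to 4FED-only responders, discrimination of 0.68 (for failure) and 0.65 (for remission) within diet falls to almost none when pooled (0.48). For other markers the pooled value remains informative but blurs the two diets. The transcript screen leaves its handling of diet unstated.

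The sizes rest on the protocol's 45%/65% rates and its nesting assumption, and the graded cases also rest on assumed shifts. Aim 2 is secondary, its model is optional in the SAP, and the randomised comparisons of symptom score and remission are unaffected. This should be fixed, but it does not undermine the trial's main conclusion.

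**What to change.** **SAP 6.2.** Fit the Phase I remission model with randomised diet and a marker-by-diet term, taking one marker or one marker score at a time. A diet main effect alone would not restore a cancelled marker. Report each marker's effect and AUROC with 95% CI separately for 1FED and 4FED, labelled exploratory. Keep the pooled model, described as a prognostic analysis.

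**SAP 5.2.2.1.** State that the transcript screen is run within diet or on the interaction.

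Restating power by diet for 292 patients would add little, since about 50 are expected.

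**Cost.** Revised wording before the database is finalised, and a few more model runs on data already planned. The drawback is wide by-diet intervals and low interaction power (about 19% to 34% for the assumed 1 to 1.5 SD markers at N = 50), so a null interaction must not be read as evidence that a marker works equally on both diets.
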